9.6.3 Laboratory Data

The actual value and change from baseline to each on study evaluation will be summarized for each clinical laboratory parameter, including hematology and clinical chemistry, for all study patients combined. In the event of repeat values, the last non-missing value per study day/time will be used.

Severity of select clinical lab measures will be determined using CTCAE criteria (e.g. those measures that have a corresponding CTCAE grade classification). Labs with CTCAE grades greater than or equal to 3 will be presented in a data listing. Shift tables that present changes from baseline to worst on-study values relative to CTCAE classification ranges will be produced.

9.6.4 Vital Signs and Physical Examinations

The actual value and change from baseline to each on study evaluation will be summarized for vital signs for all study patients combined. By-patient listings of vital sign measurements will be presented in data listings.

Physical examination results at screening will be summarized; all other abnormal physical examination data were to be recorded on the AE eCRF. All examination findings will be presented in a data listing.

9.6.5 Concomitant Medications

The use of concomitant medications will be included in by-patient data listings.

9.7 Biomarker Analysis

For the primary objective, we will analyze changes in CD8 expression before and after treatment using a paired t-test if the data are Normally distributed, and a Wilcoxon signed rank test if not. With 14 patients in each cohort, we will have 90% power (assuming 2-sided 5% alpha) to detect a 0.94^*s mean difference where “s” is the standard deviation of the differences. With all 7 cohorts combined, we will have 98 patients, which yields 90% power to detect a 0.33^*s mean difference. We will correlate CD8 expression with clinical benefit (CR/PR/SD>6m) using ROC curve analysis. With 98 patients, we would have 90% power to detect an area under the ROC curve of 0.69 (vs. 0.5 which is the null value) assuming 5% alpha and half the patients showing clinical benefit.

For the exploratory objective, we will conduct similar analyses on additional unspecified biomarkers.

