The safety data analysis for the Phase II Trial EMR 100070-003 consists of data from 88 subjects treated with 10.0 mg/kg avelumab for MCC once every 2 weeks. A total of 78 serious TEAEs were reported in 35 subjects. Fifty-seven serious TEAEs were reported as \geq Grade 3 (including 39 Grade 3 events, 7 Grade 4 events, and 11 Grade 5 events). The majority of serious TEAEs (70/78) were assessed as not related to treatment. Eight serious TEAEs in 6 subjects were considered as treatment-related: chondrocalcinosis (2 events; both Grade 2), enterocolitis (Grade 2), synovitis (Grade 2), transaminases increased (Grade 3), tubulointerstitial nephritis (Grade 2), infusion-related reaction (Grade 2), and hypothyroidism (Grade 2). In this trial, 2 cases in 2 subjects with potential irAEs were identified including a serious event of encephalopathy (Grade 2; assessed as not related to treatment) and a serious event of hypothyroidism (Grade 2; treatment-related) (12).

The clinical efficacy information summarized in the Investigator's Brochure includes data from the NSCLC and ovarian cancer expansion cohorts of the ongoing Phase I Trial EMR 100070-001, and for 20 subjects in the gastric cancer expansion cohort of the ongoing Phase I Trial EMR 100070-002. The NSCLC expansion cohort in the ongoing Phase I Trial EMR 100070-001 had a cutoff date of 15 January 2015, 6 months after start of avelumab treatment of the last subject in this expansion cohort (a total of 184 treated subjects). The objective response rate (ORR) based on confirmed and unconfirmed responses for subjects treated in the NSCLC expansion cohort was 14.1% (26 of 184 NSCLC subjects). Progression free survival (PFS) and overall survival (OS) were all evaluated for all NSCLC subjects treated in the expansion phase. As of 15 January 2015, the median PFS and OS for the NSCLC treatment expansion cohort were 11.6 weeks and 8.4 months, respectively. The clinical activity of avelumab was also evaluated by subjects' tumor PD-L1 expression status in the NSCLC expansion cohort. An objective response was observed in 20 of 122 subjects (16.4%) who were PD-L1 positive (defined as having at least 1% PD-L1 positive tumor cells) compared with 2 of 20 subjects (10.0%) who were considered PD-L1 negative (defined as having less than 1% PD-L1 positive tumor cells). A longer median PFS (12.0 vs 5.9 weeks) and OS (8.9 vs 4.6 months) were both observed in PD-L1 positive compared with PD-L1 negative subjects. The ovarian cancer

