expansion cohort had a data cutoff of 13 February 2015, approximately 13 weeks after the start of avelumab treatment on the last subject who was included in this pre-planned interim analysis on this expansion cohort. The ORR based on confirmed and unconfirmed responses for subjects treated in the ovarian cancer expansion cohort was 10.7% (8 of 75 subjects). The median PFS for the ovarian cancer expansion cohort was 11.4 weeks (95% confidence interval (CI): 6.3 to 12.0 weeks). The preliminary efficacy data for the ongoing Phase I Trial EMR 100070-002 are based on a data cutoff of 11 March 2015. As of the data cutoff, 3 of 20 subjects responded to trial treatment (all responses were partial responses [PRs] and all responses were confirmed responses), and the best overall response (BOR) was 15.0% (95% CI: 3.2% to 37.9%). The median PFS of this group was 11.9 weeks (95% CI: 6.0 to 12.3 weeks) (12).

Currently avelumab has received FDA approval for metastatic Merkel cell carcinoma and metastatic urothelial carcinoma indications (13, 14)

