7.3 Biopsy Analyses

For patients in the MTD expansion cohorts of Arms A-C, tumor tissue will be obtained pre- treatment (baseline), between Cycle 1 Day 12-15 (prior to study drug dosing), prior to Cycle 3 Day 1 study drug dosing, and at progression (if achieved stable disease \geq 6 months, partial response, or complete remission) provided there is technically biopsiable tumor, and it is safe for patient to undergo biopsy.

For patients in the escalation cohorts of Arm C (patients enrolled prior to Version 05), tumor tissue will be obtained pre- treatment (baseline), prior to Cycle 2 Day 1 dosing, and at progression (if achieved stable disease \geq 6 months, partial response, or complete remission) provided there is technically biopsiable tumor, and it is safe for patient to undergo biopsy.

For patients in the de-escalation and MTD Expansion cohort of Arm D, tumor tissue will be obtained pre- treatment (baseline), prior to Cycle 3 Day 1 dosing, and at progression (if achieved stable disease \geq 6 months, partial response, or complete remission) provided there is technically biopsiable tumor, and it is safe for patient to undergo biopsy.

Correlative studies for biomarker analyses will be performed during this study.

A fresh core needle biopsy (CNB) will be obtained solely with the purpose of research studies (pre-treatment samples) and sent to the Institutional Tissue Bank (ITB) immediately after collection. Up to 5 cores will be obtained from the CNB procedure. The number of cores obtained will be affected by the patient clinical condition at the time of biopsy and determined by the radiologist who is performing the procedure. It is important to note that in some of these trials, the biopsy sample will also be required for clinical diagnosis. In such case, the first specimen will be prioritized for clinical specimen processing. In most instances, a rapid on site evaluation (ROSE) is available locally to evaluate the adequacy of clinical sample, thus additional biopsies may be procured for this research project. Nevertheless, the amount tissue available for correlative studies can be variable. Core biopsy is typically performed using 21-18 gauge needle and with condition permitting, up to 5 cores should be collected.

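### The 90% power for the per-cohort CD8 change needs 14 complete pairs, but Section 9.7 counts 14 patients and allows for no lost samples

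*Combined protocol and SAP*

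**What the plan says.** For the primary CD8 objective, Section 9.7 (Biomarker Analysis) says "we will analyze changes in CD8 expression before and after treatment using a paired t-test if the data are Normally distributed", with a Wilcoxon signed rank test otherwise. The power statement reads "With 14 patients in each cohort, we will have 90% power" ("assuming 2-sided 5% alpha") "to detect a 0.94^*s mean difference". The pooled statement is "With all 7 cohorts combined, we will have 98 patients, which yields 90% power to detect a 0.33^*s mean difference". Section 9.7 names neither the specimen nor the post-treatment time point.

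Elsewhere in the plan:

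- **Cohort size.** Section 9.2 sets each expansion cohort at no more than 14.
- **Biopsies.** Under Section 7.3, tissue is taken "provided there is technically biopsiable tumor, and it is safe for patient to undergo biopsy", and the amount left for correlative work can vary. Arms A to C have two routine on-treatment biopsies, at Cycle 1 Day 12-15 and before Cycle 3 Day 1. Arm D has only the second.
- **Specimen.** Section 2.2.1 lists both tumor and blood as sources for the CD8 endpoint.
- **Replacement.** Section 3.3 replaces patients who leave for reasons other than toxicity or progression. Section 6.5 rules out replacement after the DLT period. Section 9.1 replaces patients who did not receive every drug in their combination. Section 9.3 mentions replacing inevaluable patients in general terms. Sections 3.3 and 6.5 do not agree with each other, but none of the four rules refers to a CD8 sample.

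**The concern.** A patient with only one usable sample contributes nothing to a paired test. The sample size in the power statement should therefore be the number of complete pairs, yet Section 9.7 uses the number of patients, and that number is also the planned cohort cap. The plan itself foresees that some biopsies will not be taken or will yield too little tissue. It gives no evaluability rate, no CD8-evaluable set, no rule for missing samples and no margin in the sample size.

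The CD8 comparison serves a primary objective. If a cohort ends with 9 or 10 pairs and shows no clear change, a reader relying on Section 9.7 would credit that result with more sensitivity than it had.

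**Working it through.** **Inputs from Section 9.7.** Paired t-test, two-sided alpha 0.05, standardised change 0.94, n = 14 per cohort; pooled n = 98 with standardised change 0.33.

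**Formula.** With n complete pairs and true mean change d·s, the test statistic follows a noncentral t distribution with n − 1 degrees of freedom and noncentrality d·√n. Power is the probability that it falls beyond ±t(0.975, n − 1).

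**Reproducing the plan.** For n = 14 and d = 0.94 the noncentrality is 0.94 × √14 = 3.52 on 13 degrees of freedom. Power is 90.1%, and the change detectable at exactly 90% power is 0.938·s. A normal approximation would give 0.866·s and a one-sided t-test 0.827·s, so the plan's figure is the two-sided paired t-test with 14 pairs. The arithmetic is right.

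**Fewer pairs.** The same formula gives:

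| Complete pairs | Power at 0.94·s | Change detectable at 90% power |
|---|---|---|
| 14 | 90.1% | 0.94·s |
| 13 | 87.5% | 0.98·s |
| 12 | 84.2% | 1.03·s |
| 11 | 80.2% | 1.09·s |
| 10 | 75.4% | 1.16·s |
| 9 | 69.6% | 1.24·s |
| 8 | 62.8% | 1.34·s |

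**Averaging over an assumed evaluability rate.** The documents give no rate. Suppose each of 14 patients independently yields a usable pair with probability r, and weight the power at each number of pairs by its binomial probability. Average power at 0.94·s is 88.1% for r = 95%, 85.8% for 90%, 80.1% for 80%, 72.9% for 70%, 64.0% for 60% and 53.4% for 50%. The chance that all 14 pairs are complete is 0.9^14 = 23% at r = 90% and 0.8^14 = 4% at r = 80%.

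**Pooled figure.** n = 98 and d = 0.33 give 89.9%, so this also reproduces, again only if every patient supplies a pair. The 98 is 7 × 14, while Section 9.2 now describes four arms with an expansion cohort each. As an illustration, 4 × 14 = 56 complete pairs give 67.9% power at 0.33·s (0.44·s detectable at 90% power). At an assumed 80% evaluability, about 45 pairs give 58.1% (0.49·s). Section 9.7 does not say whether patients treated on earlier schedules would be pooled; including them would raise these numbers.

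**The case against.** Several points on the other side have weight.

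- **Eligibility.** Section 4.1 requires biopsiable disease. That makes a baseline sample likely but does not secure the on-treatment one.
- **Blood.** The endpoint covers blood as well as tumor, and Arm D has blood draws at five scheduled times through Cycle 3 Day 1. A blood-based test should lose fewer pairs. This limits the concern but also shows why Section 9.7 must name the specimen.
- **Larger cohorts in Arms A to C.** Table 12 gives 16 patients for Arm A, and 16 and 17 treated in Arms B and C after replacements. If all could contribute, these arms could lose 2, 2 and 3 pairs and still have 14. The extra patients are not tied to sample availability, however.
- **The earlier biopsy in Arms A to C.** It reduces loss. But it is taken before the Day 15 dosing at which avelumab starts, so it answers a different question from the Cycle 3 Day 1 sample.
- **Arm D de-escalation patients.** They are also biopsied, and those treated at the same dose might be added. Section 9.7 does not say so.
- **Consequences.** No go/no-go rule hangs on the per-cohort test.

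A reader might also infer the size of the loss from the background data: "the median PFS and OS for the NSCLC treatment expansion cohort were 11.6 weeks and 8.4 months, respectively", and "The median PFS for the ovarian cancer expansion cohort was 11.4 weeks". With exponential PFS and a median of 11.6 weeks, exp(−ln 2 × 8/11.6) = 62% are progression-free at week 8, or about 8.7 of 14; the same reasoning leaves about 12 of 14 at Day 12-15. The documents do not support using these as numbers of pairs. The medians come from avelumab given alone, and the exponential shape is an assumption. Section 9.1 replaces patients who never receive avelumab, so progression before Day 15 does not reduce 14 to 12. Progression is also not loss of a biopsy: Sections 3.4, 6.2 and 7.2 allow treatment past first progression, and the first scheduled scan falls at about the same time as the Cycle 3 Day 1 biopsy.

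**Conclusion.** The point holds as one about the basis of the power statement. The calculation is correct for 14 complete pairs. The defect is that the plan equates pairs with patients at the planned cohort cap and makes no allowance for samples it expects may be missing or inadequate. From a base of 14, one lost pair takes power to 87.5%, two to 84.2%, four to 75.4% and six to 62.8%.

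How many pairs will be lost cannot be established from the documents, so these figures are a range under assumption and not a forecast. The exposure is greatest for tumor tissue in Arm D, where the only routine on-treatment biopsy comes before Cycle 3 Day 1. It is smaller for blood-based CD8, and smaller in Arms A to C. The plan should be corrected, because the statement concerns a primary objective and the change is cheap.

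**What to change.** Amend Section 9.7 as follows:

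1. Name the specimen (tumor or blood) and the post-treatment time point of the primary paired test, and define the CD8-evaluable set as patients with a usable sample at both times.
2. Replace the single 90% figure with power at 0.94·s, and the change detectable at 90% power, over a range of evaluable pairs such as 8 to 14. The table above can be used directly. Do not write in 12-pair or 9-pair expectations derived from PFS.
3. Restate the pooled figure in evaluable pairs, using the cohorts that remain instead of 7 × 14 = 98, and say which patients are pooled.
4. Report the number of complete pairs per cohort and time point beside each CD8 result.

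This is a change of wording. It needs no extra patients or procedures, and the only cost is a less favourable stated sensitivity.

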1.5 Protocol Arm Closures

In Protocol Version 07, Arm G of avelumab, radiation and cisplatin was closed due to the inability to enroll patients. Closure of Arm G was decided in the September 2018 Joint Steering Committee meeting. The protocol was revised at that time to remove all language regarding Arm G.

In Protocol Version 09, Arm E of avelumab, PF-04518600 (OX40), and radiation; and Arm F of avelumab, utomilumab (4-1BB), PF-04518600 (OX40), and radiation were closed due to emerging data, which does not support combination of two T cell agonists. Closure of Arm F was decided in the November 2019 Joint Steering Committee meeting. Closure of Arm E was decided in the January 2020 meeting between Pfizer and the PI. The protocol was revised at that time to remove all language regarding Arms E and F.

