3.0 STUDY DESIGN

3.1 Study Overview

Currently, this is a single-center, open-label, four-arm Phase I/II study of avelumab in combination with additional therapy. In Arms A, B, and C, avelumab will be administered in combination with a checkpoint agonist(s) in patients with advanced or metastatic solid tumors. In Arm D, avelumab will be administered in combination with a checkpoint agonist with radiation in patients with advanced or metastatic solid tumors.

As of Amendment Version 09, there are 4 treatment arms in this study:

- Arm A: Avelumab + Utomilumab (4-1BB)
- Arm B: Avelumab + PF-04518600 (OX40)
- Arm C: Avelumab + Utomilumab (4-1BB) + PF-04518600 (OX40)
- Arm D: Avelumab + Utomilumab (4-1BB) + XRT.

Arm D will have two phases: 1) Dose De-Escalation Phase; and, 2) Maximum-Tolerated Dose (MTD) Expansion Phase. In Arm A: Avelumab + Utomilumab (4-1BB) and Arm B: Avelumab + PF-04518600 (OX40), and Arm C: Avelumab + Utomilumab (4-1BB) + PF-04518600 (OX40), the known MTDs from the ongoing studies enrolling patients for treatment with utomilumab (4-1BB) and avelumab and PF-04518600 (OX40) and avelumab will be provided by Pfizer. Therefore, patients in Arms A-C will be enrolled on MTD expansion cohorts only in Phase I part of the study.

All study treatment arms will undergo a 28-day study cycle.

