3.2.1 Arm A: Avelumab + Utomilumab (4-1BB)

In Arm A of avelumab and utomilumab, there will be no dose escalation. The escalation of avelumab and utomilumab will be performed under a previously conducted Pfizer protocol.

The Arm A MTD expansion will enroll up to 14 patients at the established safe dose for additional safety and correlative studies to establish the RP2D for this combination.

Utomilumab will be administered at the fixed flat dose of 100 milligrams (mg) intravenously (IV) on Day 1 of each 28-day cycle or every 4 weeks. Avelumab will be administered at the fixed dose of 10 mg/kg IV on Day 15 of Cycle 1 and Days 1 and Day 15 of subsequent cycles. Premedications will be administered per institutional standard.

On days when both avelumab and utomilumab are administered, avelumab will be administered first.

Patients will be restaged at the end of every two cycles and tumor response evaluation will be based on Response Evaluation Criteria in Solid Tumors (RECIST) 1.1 and immune-related RECIST (irRECIST). Patients may be allowed to continue treatment

after two cycles of avelumab combinations if there is continued clinical response or disease stabilization and patients do not have significant toxicities. A patient may continue treatment on this combination therapy until the patient experiences confirmed disease progression, unacceptable adverse event(s), intercurrent illness that prevents further administration of treatment, and/or treatment is discontinued following investigator's decision to withdraw the patient, pregnancy, patient withdraws consent, noncompliance with trial treatment or procedure requirements, or administrative reasons.

Table 3: Dosing for Arm A: Avelumab + Utomilumab (4-1BB)

Dose Level	Utomilumab (4-1BB) IV Every 4 Weeks Starting Cycle 1 Day 1	Avelumab IV Every 2 Weeks Starting Cycle 1 Day 15
MTD/RP2D Determined by Pfizer	100 mg	10 mg/kg

As of Amendment Version 06, the avelumab dosing for Arm A was revised; therefore, a new cohort of 14 patients was enrolled.

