9.2 Statistical Methods and Properties

As of Amendment Version 09, this study will be conducted in 4 arms. Arms A, B, and C will each enroll an MTD expansion cohort. Arm D will have a dose de-escalation and MTD.

In Arm D, standard 3 +3 dose de-escalation and MTD will be applied for dose level 1 and -1 with standard MTD and DLTs rule. We will use CTCAE criteria to capture adverse events related to the study drugs. If cohort 1 is not tolerable, there will be de-escalation to cohort -1.

Each study treatment arm will have an MTD expansion cohort of up to 14 patients each. The expansion cohort for each arm will be stopped early if the aggregate DLT rate $> 33\%$ for that particular arm. The aggregate DLT rate for each arm will include patients that were treated at the same dose level in the dose escalation or de-escalation phase. If the trial does not stop early, we will estimate the disease control rate and the response rate separately for each cohort with appropriate 95% confidence intervals. We will also estimate the progression free survival (PFS) and overall survival (OS) distributions using the Kaplan-Meier product limit method and report summary measures such as the median value and probabilities at selected times (again with appropriate 95% confidence intervals).

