9.3 Sample Size Determination

During the course of the study, two to three dose levels were to be examined in each combination arm during the dose escalation/de-escalation with a standard “3+3” design, and a total of 3-6 patients will be enrolled per dose level. After each escalation or MTD determination by Pfizer, there will be an MTD expansion cohort of up to 14 patients each.

Prior to Amendment Version 05, Arm C was designed to have an escalation and 4 patients were enrolled; however, Pfizer provided recommendations for the MTD and requested that the MTD expansion commence. As of Amendment Version 06, the avelumab dosing for Arms A-C was revised; therefore, a new cohort of 14 patients each are expected to be enrolled for the MTD expansions of Arms A-C. As of Amendment Version 07, the original Arm G escalation and expansion (N= 32 total patients) cohorts have been removed from the study due to inability to accrue patients. Prior to Amendment Version 06, there was a total of 31 patients treated in the MTD expansions on the previous avelumab dosing schedule (Arm A: 8; Arm B: 12; Arm C: 11).

As of Amendment Version 08, the dosing schedules for Arms D-F were revised; therefore, Arms D, E, and F were re-initiated with the new schedule. Prior to Amendment Version 08, there were 11 patients enrolled on Arms D-F (Arm D: 4; Arm E: 3; Arm D: 4).

As of Amendment Version 09, the dosing schedule for Arm D was revised; therefore, Arm D dose de-escalation was to be re-initiated with the new schedule (2 dose levels of up to 6 patients each, or up to 12 patients total). Arms E and F were discontinued. Prior to Amendment Version 09, there were 20 patients enrolled on Arms D-F (Arm D prior to Amendment Version 08: 4 and Arm D on Version 08: 3; Arm E prior to Amendment Version 08: 3 and Arm E on Version 08: 3; and Arm F prior to Amendment Version 08: 4 and Arm F on Version 08: 3).

Thus, the planned maximum number of patients for the dose escalation/ de-escalation phase is 36 patients as indicated in Table 12. The planned maximum number of patients for the MTD expansion phase is 92 as indicated in Table 12. Therefore, the planned total maximum accrual in this study will be 128 patients (Escalation 36 + MTD

Expansions 92). Due to screen failures and replacement of inevaluable patients, up to 250 patients may be consented to this trial.

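### The pooled CD8 power statements in Section 9.7 rest on 7 cohorts and 98 patients; the current plan has four expansion cohorts of up to 14 (56), where power is 68% (paired t) and 70% (ROC), and the pool is not defined

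*Combined protocol and SAP*

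**What the plan says.** Relating CD8 expression before and after treatment to clinical benefit is a primary objective (Section 2.1.1). Section 9.7 holds its power justification, in three statements:

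- Per cohort: 14 patients give 90% power, two-sided 5%, for a mean change of 0.94 SD of the differences.
- Pooled change: "With all 7 cohorts combined, we will have 98 patients", with 90% power for 0.33 SD.
- Pooled ROC: "With 98 patients, we would have 90% power to detect an area under the ROC curve of 0.69", against a null of 0.5, at 5% alpha and with half the patients benefiting.

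The rest of the current text describes a smaller study. Section 1.5: "In Protocol Version 07, Arm G of avelumab, radiation and cisplatin was closed due to the inability to enroll patients". Section 9.3: "Arms E and F were discontinued". Section 3.1: "As of Amendment Version 09, there are 4 treatment arms in this study". Section 9.2: "Each study treatment arm will have an MTD expansion cohort of up to 14 patients each".

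Section 9.3 also counts patients from before the dosing changes. On Arms A-C, "there was a total of 31 patients treated in the MTD expansions on the previous avelumab dosing schedule". New cohorts followed in those arms; for Arm A, Section 3.2.1 says "As of Amendment Version 06, the avelumab dosing for Arm A was revised; therefore, a new cohort of 14 patients was enrolled". Section 9.3 puts the expansion maximum at 92, earlier patients included.

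**The concern.** The figure 98 is 7 × 14. It matches a design with Arms A to G, although that origin is an inference: Section 1.1 describes the initial study as having six arms. Whatever its origin, 98 agrees with no count in the current plan, and Section 9.3 was updated for the closures while Section 9.7 was not.

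The pool is also undefined. None of the four analysis sets in Section 9.1 is tied to the CD8 analysis, and Section 9.7 does not say whether earlier-schedule, replacement, escalation or de-escalation patients count. A reader cannot tell whether the pooled primary analysis has roughly two-thirds power or close to 90%, and the pool could be settled after data are seen. The choice has substance: reaching 92 mixes two avelumab schedules. Adding the Arm C escalation patients brings in an on-treatment biopsy taken before Cycle 2 Day 1, whereas the Arm A-C expansions and Arm D share one before Cycle 3 Day 1 (Section 7.3).

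**Working it through.** **Inputs.** Effects, alpha and the 50% benefit assumption come from Section 9.7; patient counts from Sections 9.2 and 9.3 and Table 12. Section 9.7 gives no sidedness for the ROC test; two-sided 5% is assumed. Every pooled patient is assumed evaluable.

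**Paired t.** Power = P(T > t₀.₉₇₅,ₙ₋₁), where T is noncentral t with n − 1 degrees of freedom and noncentrality d√n.

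- n = 14, d = 0.94: noncentrality 3.517, critical value 2.160, power 90.1%. The per-cohort statement is correct.
- n = 98, d = 0.33: 3.267, 1.985, power 89.9%. The pooled statement reproduces at its own n.
- n = 56, d = 0.33: 2.469, 2.004, power 68.0%.
- n = 92, d = 0.33: 3.165, 1.986, power 87.9%.

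**ROC.** Hanley-McNeil variance with n₁ patients benefiting and n₀ not:

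Var(A) = [A(1 − A) + (n₁ − 1)(Q₁ − A²) + (n₀ − 1)(Q₂ − A²)] / (n₁n₀), with Q₁ = A/(2 − A) and Q₂ = 2A²/(1 + A).

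Power = Φ{[(A − 0.5) − 1.96·SE(0.5)] / SE(A)}. At A = 0.69, Q₁ = 0.527 and Q₂ = 0.563.

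- N = 98 (49/49): SE(0.5) = 0.0586, SE(0.69) = 0.0534; power 92.0%. The plan's 90% is slightly conservative.
- N = 56 (28/28): 0.0778 and 0.0709; power 70.1%. A simulated Mann-Whitney test also gives 70.1%.
- N = 92 (46/46): 0.0605 and 0.0551; power 90.2%.

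**Pools the documents allow.**

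- 56: four expansions of 14.
- 63: current-schedule expansion patients in Table 12 (16 + 16 + 17) plus 14 for Arm D. Leaving out the 2 and 3 extra patients from replacement in Arms B and C gives 58.
- 75: 63 plus up to 12 Arm D de-escalation patients on the current schedule.
- 92: the stated expansion maximum, of whom 8 + 12 + 11 = 31 had the earlier avelumab schedule.
- 115 to 117: all Arm A-D patients. 92 + 4 (Arm C escalation) + 12 + 7 (Arm D current and earlier) = 115; the Table 12 rows for Arms A-D add to 24 + 28 + 32 + 33 = 117.

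| N | Paired t power at 0.33 SD | ROC power at 0.69 | SD units detectable at 90% | AUC detectable at 90% |
|---|---|---|---|---|
| 56 | 68% | 70% | 0.44 | 0.74 |
| 58 | 70% | 72% | 0.43 | 0.73 |
| 63 | 73% | 76% | 0.415 | 0.73 |
| 75 | 81% | 83% | 0.38 | 0.71 |
| 92 | 88% | 90% | 0.34 | 0.69 |
| 98 (plan) | 90% | 92% | 0.33 | 0.68 |
| 115-117 | 94% | 96% | 0.30 | 0.67 |

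**The case against.** The strongest reply is that 56 is the least favourable reading and is nowhere stated as a total, whereas 92 is. An earlier and a new cohort in each of Arms A-C, plus Arm D, also makes seven cohorts. On that reading the error is 98 against 92 and costs about 2 points of power. This stands as a limit on size: the fall to 68% and 70% holds only if the pool is four cohorts of 14. It does not rescue the text. The earlier cohorts had 8, 12 and 11 patients, so seven cohorts of 14 do not exist, and Section 9.7 does not say that two schedules are to be combined.

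Arm D de-escalation patients give tissue at the same times as Arm D expansion patients, so a 75-patient pool without the earlier avelumab schedules in Arms A-C is natural. That is fair. It gives 81% and 83%, inside the range above and still short of the claim.

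The ROC figure depends on method. At 56, other two-sided variants give 70 to 76% and one-sided tests 80 to 85%. Two-sided fits the plan's 90% at 98 better. ROC power also rests on half the patients benefiting: at an assumed 20 to 40% it is 50 to 68% for 56 patients and 71 to 88% for 92. Correcting N alone leaves that assumption untested.

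Finally, accrual follows the 3+3 rule and expansions of up to 14, and no stopping rule uses this power. That is true and limits the consequence, but the analysis serves a primary objective.

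**Conclusion.** The concern holds. The arithmetic at 98 is sound and the per-cohort statement is correct, but 98 is not a number the current plan delivers. With the four nominal cohorts, pooled power is 68% (paired t) and 70% (ROC). With all 92 planned expansion patients it is 88% and 90%, at the price of combining two avelumab schedules. Only a pool of all Arm A-D patients, or one extending to the closed arms, exceeds the stated figures. The fault lies in the stated justification and the undefined population, not in trial conduct, and should be corrected. Confidence is high on the mismatch and on the power at each N; which pool was intended cannot be determined from the documents.

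The figures assume complete sample pairs, two-sided 5% and 50% benefit. Biopsies are conditional on feasibility and safety (Section 7.3), and Section 9.7 makes no allowance for missing pairs. If 60 to 90% of patients were evaluable (an assumption), paired t power would be 46 to 63% for 56 patients and 67 to 84% for 92.

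**What to change.** In Section 9.7:

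1. Replace the seven cohorts and 98 patients with a named list of the arms, phases and dosing schedules to be pooled.
2. State whether earlier-schedule, replacement, escalation and de-escalation patients count. If Arm C escalation patients are included, say how their pre-Cycle 2 Day 1 tissue sample is handled beside the pre-Cycle 3 Day 1 samples.
3. Restate the effects detectable with 90% power for the chosen number: 0.44 SD and area 0.74 at 56; 0.415 SD and 0.73 at 63; 0.38 SD and 0.71 at 75; 0.34 SD and 0.69 at 92.
4. Give the sidedness of the ROC test, and note that the figures assume evaluable pre- and on-treatment samples and half the patients benefiting.

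The cost is SAP wording only, with no extra patients. The stated detectable effects become less favourable in every pool listed in item 3, though only marginally at 92, where earlier-schedule patients are included.
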